### Male partner procedures

Male partners of women enrolled in the study will be recruited using established recruitment methods during the initial Obumu study. These strategies operationalize protocol-specified requirements and ensure participant privacy for eligibility determination. Men will be referred to Kitebi clinic, either through invitation letters for wellness visits or standard of care clinic visits (Fig 4). Wellness visits will include provision of the following: a dual HIV and syphilis rapid test, eye exams, blood pressure checks and COVID-19 screening (and if available, COVID-19 PCR those with symptoms or antibody testing for those without symptoms). Those who are PCR positive will be referred to a medical officer for clinical evaluation and contact tracing. Men in both arms will undergo informed consent for HIV testing and referral for HIV care and ART if they test HIV-positive or offered PrEP if they test HIV-negative. Obumu male staff members will also contact male partners of women in the intervention arm of the study if their female partner gives permission. Trained research staff will counsel potentially eligible men about possible participation in the study. Men who indicate a willingness to participate in the study for 6 months will be offered an opportunity to undergo study screening. Men will have up to 6 months to enroll in the study after their female partner enrolls.

### Standard of care counseling about PrEP and ART

Participants will receive behavioral counseling on the effectiveness of ART and PrEP for men depending on their test results, and ART benefits and need for adherence during pregnancy as well as post-partum ART for the pregnant HIV positive woman. Counseling sessions will occur every 3 months, either to each partner individually or as a couple. Ad hoc sessions will be provided when requested by couples. Counselors will stress the importance of post-partum ART persistence with high adherence for clinical benefits and to prevent onward HIV transmission to breastfeeding infants and sexual partners.

**Table 2. Components of HIV prevention delivery for HIV serodiscordant couples in PMTCT B+ with integrated ART and PrEP**

SOC services for HIV serodiscordant couples	Additional components of integrated PrEP with PMTCT B+
Behavioral counseling	Couples: counseling on HIV serodiscordance & efficacy of integrated PrEP and ART for (enrollment)
Condom provision	HIV-positive women: counseling on post-partum ART continuation & adherence for women (antenatal visits, 3 and 6 months post partum)
PrEP counseling & provision	HIV-negative men: counseling about PrEP benefits & adherence (enrollment, quarterly visits at months 3 and 6)
6-monthly CD4 testing	HIV-negative men: assessment of acute HIV infection, PrEP provision HIV-positive women: HIV RNA testing (6 months post-partum)
Annual HIV RNA testing,	HIV negative men who initiate PrEP: baseline and 6-monthly renal function monitoring, urine for tenofovir testing at 3 & 6 months HIV-positive men: assessment of ART use

Counselors will assess men's willingness to initiate PrEP or ART, willingness of women to continue ART post-partum, strategies to maintain daily adherence to PrEP and ART, the time-limited use of PrEP, other HIV risk reduction strategies (condom use, medical male circumcision, and treatment of sexually transmitted infections), and couple communication. Male partners will be supported to make informed choices. Acute HIV symptoms will be assessed before PrEP dispensation. Medication refills with 3-month supplies, ART and PrEP adherence counseling, condoms, HIV testing, and lab monitoring

(6-monthly creatinine, CD4 and HIV RNA testing) will be provided (Table 2).

#### PrEP medication and dispensation

PrEP will be offered to HIV-negative men according to national guidelines (47), and with the recommendation to take it for 6 months after their partner starts ART or until she is virally suppressed. Male partners will be assessed for acute HIV infection, counseled on PrEP and offered PrEP, if it is desired and there are no acute HIV symptoms, and they test HIV negative on rapid HIV tests. PrEP will be dispensed in a 3-monthly supply. HIV testing will be conducted at months 3 and 6 prior to providing PrEP refills. PrEP use will be suspended if HIV tests are positive or if acute HIV infection is suspected. Renal monitoring will occur at baseline and 6-months for men who initiate PrEP.

The study will provide open-label PrEP to HIV-negative male partners for 6 months or until their HIV-positive female partner is virally suppressed. Co-formulated FTC/TDF at 200 mg / 300 mg respectively will be used. The dose of FTC/TDF is the standard dose approved by the U.S. Food and Drug Administration. The study drug will be stored in accordance with the drug manufacturer's recommendations. The pharmacy and storage facility will have locked, climate-controlled environments, with controlled humidity and temperature to remain within limits allowed by the manufacturer for drug storage. Counseling on the medications being used, their side effect profiles, how to take the study medication, what to do if side effects are experienced, and the importance of not sharing study medication to optimize potential efficacy will be provided.

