- Design:** Randomized clinical trial  
Up to 6 months of post-partum follow-up
- Population:** 200 HIV-positive pregnant women who have a partner of unknown status and their male partners
- Study Site:** The Infectious Diseases Institute (IDI) Kasangati and Kitebi Health Center III antenatal care (ANC) clinic in Kampala, Uganda
- Approach:** We will recruit pregnant women  $\geq 18$  years accessing ANC and PMTCT B+ programs in Kampala, who have a male partner of unknown HIV status. Women will be randomized 1:1:1:1 to the intervention for male partners (provision of an invitation letter for a wellness visit with dual rapid syphilis and HIV tests, blood pressure, visual acuity screening and COVID-19 symptom screening or an invitation letter for fast track testing at the clinic (the standard of care), and either the intervention of POC VL and same day ART adherence counseling or the standard of care every six months lab-based HIV VL testing. with adherence counseling at their next visit.
- In accordance with MOH guidelines, women in both arms will be offered an HIVST to bring home to their partners. In both arms, women will be instructed in the use and interpretation of HIVST and be provided up to two HIVST kits to give to or use with their male partners, per Ugandan Ministry of Health guidelines. After HIV testing and enrollment into the Kingasa study, HIV-negative male partners will be offered PrEP and HIV-positive men will be linked to ART. We will recommend that HIV-negative men take PrEP until their partner has been on ART for at least 6 months or longer if they report additional partners of unknown status.
- Aim 1:** To evaluate whether the proportion of male partners of pregnant HIV-positive women who test for HIV, is improved after distribution of a letter of invitation to a wellness visit (dual syphilis and HIV rapid test, blood pressure, visual acuity screening and COVID-19 screening) to their female partners compared to the standard of care (standard of care invitation letter from the clinic).
- Aim 2:** To evaluate whether POC viral load testing with same day ART adherence support improves viral suppression among pregnant and post-partum women living with HIV compared to standard of care lab-based HIV VL testing.

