We will encourage men who test HIV-negative to use PrEP until their partner has achieved viral suppression (typically six months). However, all HIV-negative men will be offered PrEP, and men who test HIV- positive will be encouraged to start ART. Per recent Ugandan MOH guidelines, women in both arms will be provided HIVST kits for their partners with self-instruction materials about HIVST, encouragement to seek confirmatory testing and counseling, and brief educational materials about PrEP and ART, along with instruction in the use and interpretation of HIVST.

All women and men in the cohort will be screened for COVID-19 symptoms.

The primary endpoint of the randomized intervention for male partners is the proportion of male partners who test for HIV at the clinic, during the study. The primary analysis is an intent to treat comparison by randomization arms (comparing Arms 1 and 2 combined to Arms 3 and 4 combined) of the proportion achieving the primary outcome. The secondary outcome is engagement in care of the male partners, defined as 1) for HIV-negative men initiating PrEP within six months of randomization of their HIV-positive partner is randomized, and 2) for HIV-positive men, initiation of ART within 6 months after their HIV positive partner is randomized. Quantitative and qualitative methods will be used to assess acceptability of dual syphilis and HIV testing, blood pressure, visual acuity screening, and COVID-19 screening as part of wellness visits for male partners whose partner was randomized to the intervention arm, PrEP among male partners who test HIV negative, ART among male partners who test HIV positive, and identify ways to minimize social harms through antenatal programs that try to reach men.

The primary endpoint of the randomized intervention for pregnant women with HIV is viral suppression at 6 months post-partum. The primary analysis is an intent to treat comparison by randomization arm (arms 1 and 3 combined compared to arms 2 and 4 combined) of the primary outcome, of the proportion of women living with HIV who are virally suppressed at 6 months post-partum by arm, as the measure of continuation of ART and high adherence post-partum.

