### *Recruitment*

IDI Kasangati has long-established recruitment and retention strategies to identify and enroll participants for prospective follow up. Recruitment materials will be approved by the IRB before study initiation. Recruitment materials will educate women about the benefits of male partner testing, the probability of being HIV serodiscordant, safety and efficacy of PrEP, and risks of post-partum ART discontinuation for the woman's health and the possibility of HIV transmission to her baby and partner.

Women attending antenatal care are offered HIV testing, and those who test positive are provided immediate ART according to Uganda national HIV treatment and prevention guidelines. Approximately, 50 HIV-positive women are identified per month. IDI Kasangati will work directly with the Kitebi KCCA facility, including antenatal care/PMTCT programs, to identify pregnant HIV-positive women attending PMTCT B+ services. Health care workers and study staff at Kitebi ANC clinic will provide general information sessions to inform potential participants.

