### **Power to detect a difference in viral suppression in female partners with 200 women**

Assuming 60-80% of pregnant women in Kingasa will be virally suppressed at 6 months post-partum in the standard of care arm (which is lower than Obumu due to the impact of COVID-19 on women’s ability to leave home for ART refills and adherence among women who have not disclosed), we have 80% power with a two-sided alpha of 0.05 to detect an 13-18% increase in viral suppression as a result of the POC VL test (Table 4). The primary analysis for effectiveness of male testing will compare Arms 1 and 2 combined compared to Arms 3 and 4 combined, the primary analysis for effectiveness of POC VL and targeted adherence will compare the two groups with and without POC VL (i.e. Arms 1 and 3 combined compared to Arms 2 and 4 combined). An intention to treat approach will be used.

Aim 1:	Probability of outcome in SOC conditions	Outcome change that can be detected with 80% power	Aim 2:	Probability of outcome in SOC conditions	Outcome change that can be detected with 80% power
Outcome: Male Partner tested for HIV (N = 200)	20%	22%	Outcome: VS of the women at 6 months post-partum	60%	18%
	25%	21%		70%	16%
	30%	20%		80%	13%

The analysis for HIV testing in the male partner will use Kaplan Meier methods to estimate the proportion of women who have their male partner tested during the study, using time from the women’s enrollment until her partner tests. The proportion will be assessed at 6 and 12 months as the survival curve estimate at the end of the visit window. A log-rank test will be used to evaluate the difference between arms in proportion tested. The analysis for VS at 6 months post-partum will use logistic regression to assess the odds of VS at the 6-month post-partum visit.

Outcome measurements

Aim 1: The outcome for Aim 1 is the proportion of men who come to the ANC clinic to test for HIV in the intervention arm compared to those randomized to the control arm, including whether they initially used a HIVST before coming to the clinic.

Aim 2: The outcome for Aim 2 is viral suppression at 6 months postpartum, assessed at this visit.

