### Benefits

The primary aim of this study is to evaluate the impact of innovative strategies on male partner HIV testing, engagement in HIV care and prevention among men, and on post-partum ART continuation and adherence among HIV-positive women. HIV prevention practices, according to Ugandan guidelines, will be provided to all participants enrolled in this study. This will include risk reduction counseling, treatment of sexually transmitted infections, condoms, and referral for medical male circumcision. If prevention strategies are modified during the course of study conduct (e.g. PrEP becomes available through the public health system), participants will be counseled and referred for these strategies as well.

Women in the study will benefit from male partner testing, facilitated disclosure and ART counseling. HIV-negative male partner participants will benefit by having free access to PrEP during the study period, until 6 months after their partner initiates ART. Participants may benefit from ongoing access to prevention services. There may be no other direct benefits to participants in this study. However, participants and others also may benefit in the future from information learned from this study.

All participants will be provided with HIV prevention services, including condoms, STI treatment, and ongoing support, including counseling and referral to other support services. Men in the intervention arm will be provided with additional health services as part of the wellness visit.

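### The advice on how long men should take PrEP, and the description of study supply, disagree when the female partner is still viremic after 6 months of ART

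*Protocol*

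**What the plan says.** Three statements advise men how long to take PrEP:

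- Summary, Approach: men are recommended to "take PrEP until their partner has been on ART for at least 6 months or longer if they report additional partners of unknown status".
- Overall design: men who test negative are encouraged "to use PrEP until their partner has achieved viral suppression (typically six months"). The same paragraph adds that "all HIV-negative men will be offered PrEP".
- PrEP medication and dispensation, opening sentence: the recommendation is to take it "for 6 months after their partner starts ART or until she is virally suppressed".

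Three places describe what the study supplies:

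- PrEP medication and dispensation, second paragraph: open-label PrEP is provided "for 6 months or until their HIV-positive female partner is virally suppressed".
- Benefits: men have "free access to PrEP during the study period, until 6 months after their partner initiates ART".
- Table 6: PrEP provision is marked at enrollment, M3 and M6 for HIV-negative men, with no condition attached.

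The Final study visit section follows men for 6 months from their own enrollment and then refers those on PrEP to programs where it is available.

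**The concern.** Overall design treats six months as the typical time to suppression, so the time criterion and the suppression criterion look interchangeable. They separate when the partner has had 6 months of ART and is still viremic. That man is still exposed, and the protocol's own account of PrEP as a bridge (Background, on the integrated PrEP and ART strategy) has PrEP covering the period before she is suppressed.

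The section on standard of care counseling has counselors discuss the limited duration of PrEP with men, who then choose. On the present text, two counselors could give this man opposite advice and each cite the protocol. The Benefits statement adds a second difficulty: its limit runs from her ART start, while his visits run from his own enrollment.

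**Working it through.** There is no plan figure to reproduce. The check applies each statement to the same cases and then compares the two clocks.

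**1. Statements side by side**

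| Place | Kind | Partner viremic after 6 months of ART | Partner suppressed before 6 months of ART |
|---|---|---|---|
| Summary, Approach | advice | floor reached; viremia is not a stated reason to go on | continue to 6 months |
| Overall design | advice | continue | may stop |
| PrEP section, recommendation | advice | earlier limit: stop; later limit: continue | earlier limit: stop; later limit: continue to 6 months |
| PrEP section, supply | supply | depends on the ordering, and on when the 6 months start, which is not stated | same |
| Benefits | supply | free access has ended | free access to 6 months |
| Table 6 | supply | provided at enrollment, M3, M6 | provided at enrollment, M3, M6 |

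The advice statements agree without further interpretation only if suppression arrives at about 6 months of ART. A rule that requires both criteria satisfies the Summary and Overall design in both columns, and it is one of the two readings the PrEP section already allows.

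**2. The two clocks**

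Let *a* be the months the woman has been on ART at her enrollment, and *e* the months from her enrollment to his. Male partner procedures allow *e* from 0 to 6. Eligibility does not require newly started ART, and the Antenatal and postnatal care section treats women newly initiating ART as a subset, so *a* can exceed 0. For women diagnosed in antenatal care, *a* should be small, because "those who test positive are provided immediate ART according to Uganda national HIV treatment and prevention guidelines".

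Free access left under Benefits when he enrolls = max(0, 6 − *a* − *e*) months. Table 6 covers 6 months from his enrollment in every case.

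- *a* = 0, *e* = 0: 6 − 0 − 0 = 6 months. Benefits and Table 6 agree.
- *a* = 0, *e* = 6: 6 − 0 − 6 = 0 months, against 6 in Table 6.
- *a* = 6, *e* = 0: 6 − 6 − 0 = 0 months, against 6 in Table 6.

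So, read literally, the Benefits limit can run out before a man has had any study PrEP.

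**3. Can the affected group be sized?**

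The nearest figure is the Aim 2 planning assumption: "Assuming 60-80% of pregnant women in Kingasa will be virally suppressed at 6 months post-partum in the standard of care arm". That leaves 1 − 0.80 = 20% to 1 − 0.60 = 40% not suppressed. It shows that suppression cannot be taken for granted, but it is a planning range at 6 months post-partum, not a viremia rate at 6 months of ART. Time since starting ART is also not time on ART if she has interrupted treatment, and that visit can fall after his follow-up has ended.

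The Aim 1 planning values give 100 × 0.20 + 100 × 0.42 = 62 to 100 × 0.30 + 100 × 0.50 = 80 tested men. Taking the counseling message that about half of partners differ in status, 31 to 40 would be HIV-negative. Those are men who would hear the advice, not men who meet the conflict. The protocol gives no figure that turns either range into a count of affected men.

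**The case against.** The strongest reply is that these statements answer different questions. Three are advice and the others concern supply, so they are not competing stop rules. The Summary gives a minimum, which permits longer use. The only instruction to suspend PrEP is for a positive HIV test or suspected acute infection. Table 6, the offer to all HIV-negative men and referral at exit mean that a man with a viremic partner can get PrEP throughout his follow-up. All of this stands, and it keeps the priority low. It does not tell a counselor what to recommend in the viremic case, and it does not reconcile Benefits with Table 6.

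A second reply is that requiring both criteria is a policy choice. That is partly right: it keeps some men on PrEP after early suppression, where Overall design would let them stop. It is nonetheless the one rule that honors both the Summary's minimum and Overall design's suppression condition. A related caution also stands. The limit of 50 copies/mL is used for the Aim 2 outcome and for managing the woman's ART, and a limit of 200 triggers extra counseling, but no section ties either to stopping PrEP. The cut-off for this purpose therefore has to be chosen. Making her result govern his advice adds no new dependency, since two sections already do so, but counselors remain bound by the Confidentiality section where she has not disclosed.

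A reader might infer that the study withdraws drug from exposed men, that 20–40% of men are affected, or that Aim 3 is compromised. The documents support none of these. Supply in Table 6 is unconditional, the 20–40% describes women at a different time point, and Aim 3 counts initiation of PrEP, not its duration.

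**Conclusion.** The inconsistency is real and can be read directly from the text. For a partner still viremic after 6 months of ART, Overall design says continue, the PrEP section can be read either way, the Summary's minimum has been met, and Benefits ends free access. For a woman already on ART, or a man who enrolls late, the Benefits limit also conflicts with Table 6.

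This is a low-priority correction that protects participants. It matters for consistent advice and for a truthful statement of supply; no loss of study drug is shown. The number of men affected cannot be derived from the protocol. No endpoint, denominator or power figure changes. The conclusion assumes only that some women remain viremic after 6 months of ART, or were on ART before enrollment, and the protocol excludes neither.

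**What to change.** (a) Advice. In the Summary, Overall design and the first sentence of PrEP medication and dispensation, use one rule: PrEP is recommended until the partner has had at least 6 months of ART and has a documented suppressed viral load, and longer if he has other partners whose status is unknown. The investigators, or the national guidelines they follow, should set the suppression cut-off for this purpose.

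(b) Supply. In the second paragraph of PrEP medication and dispensation and in Benefits, state that study PrEP is available through his M6 visit as in Table 6, with referral afterwards as in Final study visit. Delete the limit of 6 months after her ART start.

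Leave the offer to all HIV-negative men and the Aim 3 outcome as they are.

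The cost is wording in four sections and the counseling script, with no tests, visits or drug beyond those already scheduled. Some men would stay on optional PrEP somewhat longer. This would occur mainly in the laboratory viral-load arms, where results are returned at the next visit and Table 5 schedules the laboratory test only antenatally, as indicated, and at 6 months post-partum.

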#### PrEP adherence

High adherence is important for PrEP effectiveness in preventing HIV acquisition. Study staff also will provide brief adherence counseling at each scheduled visit, to mimic "real world" counseling. Data on adherence to the product use regimen will be collected via standardized interviewer-administered questions to ascertain product use. PrEP use will be measured by dispensing records, and self-report through a validated 3-item questionnaire. Clinic and pharmacy records will be used to document PrEP prescriptions at the ANC clinics and IDI Kasangati, abstracted in real time from pharmacy records and entered into an electronic database. Adherence will also be assessed through urine tenofovir drug levels in male partners 3 and 6 months after PrEP initiation. These point of care kits provide an inexpensive and accurate alternative to plasma or DBS to quantitatively measure adherence.

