#### Final study visit

Women will be followed for 6 months post-partum and male partners will be followed for 6 months after enrollment into the study. At this time, or when a participant discontinues study participation, they will have a final study visit. Study procedures at this visit will be similar to other follow up visits. All study participants on ART will continue receiving care at a public health clinic of their choice. Participants on PrEP will be referred for PrEP where available through demonstration projects or the public health system.

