*PrEP medication.* Risks and side effects related to PrEP occurring in a minority of individuals taking PrEP - gastrointestinal intolerance, such as nausea, diarrhea or vomiting, flatulence; rare but serious - lactic acidosis/ severe hepatomegaly with steatosis, renal impairment, including cases of acute renal failure and Fanconi's syndrome (renal tubular injury with severe hypophosphatemia), increase in bone metabolism leading to osteopenia, hypersensitivity reaction.

*Informal Focus Group Discussions.* The risks of participating in the informal focus group discussions are minimal, and participation is voluntary. It is possible that participants might become tired during the focus group. They may also find some of the questions uncomfortable or hard to answer. Participants can choose to leave the focus group discussion at any point.

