**Table 6. Procedures for male partners**

[ ] as indicated

\*Three months after study enrollment

	E	M3*	M6
ADMINISTRATIVE AND REGULATORY PROCEDURES			
Obtain written informed consent	X		
CLINIC PROCEDURES			
Provide HIV test results and post-test counseling	X		
Medical history	X		
Perform physical exam	X	[X]	[X]
STI syndromic assessment and management	X	[X]	[X]
Dual syphilis-HIV rapid test (intervention arm only)	X	X	X
Blood pressure screening (intervention arm only)	X	X	X
Visual acuity screening (intervention arm only)	X	X	X
COVID-19 screening and if available, testing (intervention arm only)	X	X	X
Syphilis testing (control arm)	X	X	X
HIV-NEGATIVE MEN			
Provide HIV test results		X	X
Hepatitis B surface antigen	X		
Creatinine	X		[X]
PrEP provision	X	X	X
HIV-POSITIVE MEN			
Referral for / provision of ART according to national guidelines	X	X	X
Assess ART use and linkage/retention in care		X	X
POC HIV viral load with same day ART adherence counseling*	X		X

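### Table 6 schedules three 3-month PrEP supplies (9 months), while the protocol states 6 months of study PrEP and ends the man's follow-up at month 6, so no study contact is scheduled during the last supply

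*Protocol*

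**What the plan says.** **Supply.** Under PrEP medication and dispensation: "PrEP will be dispensed in a 3-monthly supply". The same section adds: "HIV testing will be conducted at months 3 and 6 prior to providing PrEP refills". Table 6 (procedures for male partners) lists "PrEP provision X X X", that is, at enrollment, M3 and M6. None of the three marks is bracketed, although the table uses brackets elsewhere for procedures done only as indicated.

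**Duration and end of follow-up.** PrEP medication and dispensation also gives the length of study-provided PrEP as 6 months, or until the female partner is virally suppressed. Final study visit has men followed for 6 months from their own enrollment and then closes out: "Participants on PrEP will be referred for PrEP where available through demonstration projects or the public health system". Table 6 has no column after M6.

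**Monitoring.** "Renal monitoring will occur at baseline and 6-months for men who initiate PrEP" (PrEP medication and dispensation). Table 2 likewise gives baseline and 6-monthly renal monitoring for men who start PrEP. Table 6 shows creatinine unbracketed at enrollment but bracketed at M6. PrEP adherence calls for "urine tenofovir drug levels in male partners 3 and 6 months after PrEP initiation", whereas the Table 6 footnote counts M3 from study enrollment. PrEP safety asks for serious adverse events and PrEP-related events of Grade 3 and above, without giving a collection window. Risks lists "renal impairment, including cases of acute renal failure" among the rare but serious harms of PrEP.

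**The concern.** Site staff at a man's M6 visit have conflicting directions. Table 6 and the month-6 refill sentence tell them to dispense. The stated 6-month duration and the close-out referral suggest that study supply has ended and that only a hand-over remains. The hand-over itself is conditional on local availability.

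If they dispense, the man leaves with 3 months of study drug and no further scheduled study contact. The protocol undertakes to collect serious and higher-grade PrEP-related events, but nothing is scheduled that would bring a new event in that period to the study's attention.

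Two smaller mismatches sit beside this. The tenofovir checks and the visit schedule use different time origins. The M6 creatinine reads as fixed in the text and as optional in the table.

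**Working it through.** **Inputs.** Supply per dispensing: 3 months (PrEP medication and dispensation). Scheduled dispensings: months 0, 3 and 6 from enrollment (Table 6). Last study visit: month 6 (Final study visit). Stated length of study PrEP: 6 months, or until partner suppression (PrEP medication and dispensation).

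**Reproducing the stated 6 months.** Months supplied = number of dispensings × 3.
- Enrollment and M3 only: 2 × 3 = 6 months. This equals the stated duration, and 0 months fall after M6.
- Table 6 as written: 3 × 3 = 9 months. This does not equal 6.

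This shows only which schedule matches which figure, not which one is right.

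**Supply falling after the final visit.** The M6 supply covers months 6 to 9, so 3 months fall after M6 whenever it is dispensed. Share after M6 = 3 ÷ months supplied.

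| First dispensing | Months supplied | After M6 | Share |
|---|---|---|---|
| Enrollment | 9 | 3 | 3/9 = 33% |
| M3 | 6 | 3 | 3/6 = 50% |
| M6 | 3 | 3 | 3/3 = 100% |

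One third is therefore the figure for a full course from enrollment, not a ceiling.

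**Tenofovir checks.** Let s be the months from enrollment to PrEP start. Checks dated from initiation fall at s + 3 and s + 6, and follow-up ends at month 6.
- s = 0: checks at months 3 and 6, both within follow-up.
- s = 3: checks at months 6 and 9. The second falls 3 months after follow-up ends.
- s = 6: checks at months 9 and 12. Neither is reached.

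The 6-month check can be done within follow-up only if s = 0. The renal sentence names baseline and 6 months without giving an origin, so the same conflict cannot be shown for creatinine.

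**M6 creatinine.** The text and Table 2 state it for every man who initiates PrEP. Table 6 brackets it, in a row that covers all HIV-negative men, including those who decline PrEP.

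**The case against.** The strongest reply is that this is a wording conflict and not a gap in safety design. Most of that stands.

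- **HIV and renal testing.** A reader might infer that a third of the drug is taken with HIV and creatinine checks missed. The protocol's own intervals do not support this for a man who starts at enrollment. He is tested for HIV at M6 before the refill, so the next 3-monthly test falls due at month 6 + 3 = 9, when that supply runs out. With 6-monthly creatinine, the next falls due at month 6 + 6 = 12.
- **Acting on an abnormal M6 result.** A reader might infer that nobody could act on it. The Retention section provides for home visits after an abnormal test result, and no creatinine turnaround time is given.
- **Adverse events.** PrEP safety sets no collection window, follows reported events until they resolve or stabilize, and seeks outside records for serious events. The end of detection is therefore inferred from the end of scheduled visits. It would be too strong to say that events after M6 cannot be captured.
- **Safety analysis.** The protocol describes no safety summary based on dispensed drug as exposure, so there is none to be distorted.
- **Head count.** A reader might multiply expected testers by the 97% PrEP uptake quoted in the background. That figure comes from couples who had already disclosed to each other, which the protocol itself names as the primary difference. The sum would also ignore men whose supply ends because the partner is suppressed. No count is offered here.
- **The creatinine bracket.** It may only reflect that the row includes men not on PrEP.
- **The duration clause.** It might be read as whichever limit comes later, which would make the M6 supply one for men whose partner is not yet suppressed. The clause does not say so, and the Table 6 mark is not conditional.

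None of this reconciles 9 months with 6, or an M6 refill with a close-out referral.

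**Conclusion.** The conflict is real and is wrong as written. Table 6 and the month-6 refill sentence imply 9 months of study drug for a man starting at enrollment, against a stated 6 months (or until partner suppression) and a final visit at M6. The part falling after the last scheduled study contact is 3 months: one third of supply for a start at enrollment, one half for a start at M3, and all of it for a start at M6. What is missing during that supply is a scheduled contact to detect new adverse events. The documents do not show that HIV or renal checks fall overdue for a man who starts at enrollment.

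The tenofovir mismatch also holds: any man who starts after enrollment leaves before his 6-month check. The creatinine bracket is an ambiguity to clear up and not an established contradiction.

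The figures assume visits on schedule, a full 3-month supply each time, use without gaps, and no earlier stop because of partner suppression. Neither primary endpoint is touched, and Aim 3 counts PrEP initiation only. The point concerns drug supply and safety contact at the end of the study.

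**What to change.** Reconcile Table 2 and its accompanying text, PrEP medication and dispensation, PrEP adherence, Final study visit and Table 6, so that they agree on four things:

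1. The duration of study PrEP, the M6 provision mark, the month-6 refill sentence and the final-visit referral should describe one arrangement, including how the 6-month and partner-suppression limits combine.
2. If an M6 supply is kept, state what study safety contact covers it.
3. Use one time origin for the tenofovir checks, and say what applies to men who start PrEP after enrollment.
4. State whether the M6 creatinine is fixed for men on PrEP, for example by separating them from non-initiators in the Table 6 row.

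Which rule is right in each case is for the investigators. The cost is a wording amendment in these places, plus whatever contact they specify if supply at the final visit is retained. Sample size, randomization and the primary analyses do not change.
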